3.5. Secondary Clinical Outcomes

The **secondary clinical outcomes** are:

1. length of stay in hospital
2. length of oxygen therapy
3. health care costs including transport costs and social opportunity costs (including back transfer)
4. sustainability and adherence to the respiratory care bundle beyond the intervention period measured with the Normalisation Process Theory
5. measurement of the proportion of infants and children transferred to a tertiary hospital post implementation
6. consumer satisfaction survey – includes staff and parents/carers

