7. DATA

7.1 Data Collection

The precise data to be collected and their sources for the study are given as per the below Clinical Research Forms (CRF) and datasets:

CRF 1	Clinical data
Source for Clinical data: Patient’s medical records, including observations and medical/nursing notes, discharge summary and admission form. Includes EDIS export to locate the relevant patients to obtain data from.	
CRF 2	Health Economy data (specifically aimed at out-of-pocket costs for families and measures of quality of life)
Source for Health Economy data: Use of the GenPrem instrument will be for the parent as proxy for the child and as the parent for their own experience with their child’s admission to hospital.	
CRF 3	Implementation Science data (specifically aimed at knowledge, skill retention and fidelity)
Source for Implementation Science data: The Normalisation Process Theory tool will be used and adapted for the staff survey. This survey will be in paper and electronic format depending on what is most suitable for the local team.	

Other Datasets & Collection includes:

Health Economy data (specifically aimed at health care and transportation costs) – sourced as per current Qld Health per day admission costings for the ward and/or Intensive Care and transfer/retrieval costs.

Health Economy data (specifically aimed at implementation costs which includes education costs) – sourced by capturing all education records and monitoring/capturing data on the movement of the transient staff in these regions.

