Data will be collected in an online REDCap database. In each site the emergency admissions will be screened for children 0-4 years of age presenting with respiratory symptoms. Data on the baseline demographics, physiology at presentation and initial medical management will be captured. Length of hospital stay, length of oxygen therapy, type of oxygen therapy, and amount of oxygen resources will be captured. Further information will be captured on methods of oxygen therapy. Adverse events will be recorded. For children who required transfer to high level of care, vital signs and clinical diagnosis and medical therapy provided at time of decision to transfer will be collected. Data on respiratory support during transfer, mode and length of transport and data on treatment in accepting hospital and length of hospital stay will be collected. Adherence to the respiratory care bundle will be measured by the number of frequency of deviations from the protocol.

Twelve parents per hospital using a face-to-face structured interview will complete a paediatric proxy health related quality of life measurer (PedsQL).

Historical Control. Admissions (HBCIS) to the participating hospitals in year 2016-2022 will be screened using the same screening log as in the main protocol (Year 2020-2022 will be separately analysed due to impact of COVID-19 pandemic) and the same data collection as above used.

Time Points for Data Collection. All physiological (heart and respiratory rate, temperature) and blood parameters (arterial gases) that are captured in the medical records during the hospital admission and where relevant during the transfer for higher level of care. If admitted to a tertiary hospital, data on respiratory support provided will be captured.

Specific data

The specific data set mirrors in its basic form the data captured in our previous 3 large RCT's using nasal high-flow in children with ARF or bronchiolitis. Additional data on out-of-pocket expenses and lost income will be recorded.

Background data:

Background data collection will be collected as per the CRF. Below outlines some of the specifics which continue the same data collection of the 3 large RCT's.

Demographics:

- Age (on admission)
- Gender
- Weight (on admission)
- Ethnicity
- Diagnosis at admission
- History and risk factors
 - Prematurity (<37 weeks at birth)
 - Previous neonatal respiratory support post delivery
 - Previous Intensive Care admission post delivery

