Consumer satisfaction: Data on consumer satisfaction with 12 parents/carers per hospital using a face-to-face structured interview with local clinical staff will be recorded with the GenPrem instrument. The GenPrem is an 8 dimension, 41 item. Patient reported experience measure which explores the domains of Convenience; Communication; Quality; Environment and facilities; Integration; Involvement; Discomfort; and Patient-centred care.

Evaluation of the Implementation outcomes measures:

Implementation Outcomes	Data analysis
Implementation outcomes	Society for the Implementation Research Instrument tool kit.
Use of EBP as a routine treatment locally.	SIRC acceptability measure.
Feasibility of the implemented changes.	SIRC Feasibility measure.
Acceptability of the EBP.	SIRC Adoption measure.
Satisfaction with the use of EBP (all stakeholders).	SIRC Penetration, Adaptability, and Sustainability measures.
Satisfaction with the implementation process.	SIRC Engaging measures (implementation leaders, opinion leaders, champions, external agents).
Evaluation of the EBP implementation is good.	SIRC Executing, Planning, Reflecting and Evaluating Measures.
Recommended for further implementation in other healthcare settings.	SIRC satisfaction and client outcome measures.
Service/Research Outcomes	
Satisfaction with education and competencies associated with AFR management.	SIRC Knowledge and beliefs about the intervention, Individual stage of change, Self-efficacy, Individual stage of change.
Aeroevacuation use is reduced.	Cost analysis of reduced high intensity care.
Electronic medical record prompts are operational.	Audit of electronic records.

Economic evaluation of implementation process

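### Three of seven implementation outcomes are paired with another construct's instrument, and post-study adherence is assigned only to a staff survey

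*Protocol*

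**What the plan says.** Section 3.7 lists seven implementation outcomes and says that the SIRC toolkit will cover acceptability, feasibility, adoption, penetration, adaptability and sustainability, among other measures. The table in section 8.3 then assigns a measure to each outcome. "Use of EBP as a routine treatment locally" is given the "SIRC acceptability measure". Acceptability of the practice is given the "SIRC Adoption measure". Satisfaction of all stakeholders with its use is given the "SIRC Penetration, Adaptability, and Sustainability measures". The toolkit's satisfaction measure stands further down, against recommendation to other settings.

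Section 3.5 item 4 is "sustainability and adherence to the respiratory care bundle beyond the intervention period measured with the Normalisation Process Theory". Section 7.1 (CRF 3) says that the Normalisation Process Theory (NPT) tool will be adapted for the staff survey. Section 7.1 also says "Adherence to the respiratory care bundle will be measured by the number of frequency of deviations from the protocol", and section 8.3 repeats this. Section 7.2 adds a six-monthly audit of actual against recommended practice within the 31-month phase.

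Section 7.1 describes CRF 2 as "Health Economy data (specifically aimed at out-of-pocket costs for families and measures of quality of life" and names GenPrem as its source. Section 8.3 calls GenPrem a "Patient reported experience measure which explores the domains of Convenience; Communication; Quality; Environment and facilities", followed by four further domains.

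**The concern.** Apart from the general list in section 3.7, the section 8.3 table is the only place where the protocol says which instrument answers which implementation outcome. An analyst who followed it would report an adoption score as acceptability, an acceptability score as routine use, and penetration or sustainability scores as satisfaction. A bundle that staff like but seldom use could then appear as routine practice. This bears on stated aims. Objective 3 is about staff acceptance and compliance, and section 6.2.3 describes a hybrid design that assesses effectiveness and implementation together.

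The adherence item has a similar fault. Whether care follows the bundle after the study team withdraws is a question about what was done for patients. A staff survey built on NPT gives staff views of how far the practice is embedded. Reporting those views as adherence would answer a different question, and objective 4 depends on this period.

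**Working it through.** No arithmetic applies, because the point rests on no rate, power or sample size. The check sets the entries side by side.

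**The table in section 8.3, row by row**

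| Row | Outcome | Measure assigned | Match by name |
|---|---|---|---|
| 1 | Routine use | Acceptability | No |
| 2 | Feasibility | Feasibility | Yes |
| 3 | Acceptability | Adoption | No |
| 4 | Satisfaction with use | Penetration, adaptability, sustainability | No |
| 5 | Satisfaction with the process | Engaging | Not counted |
| 6 | Evaluation of the implementation | Executing, planning, reflecting, evaluating | Not counted |
| 7 | Recommended elsewhere | Satisfaction, client outcome | Not counted |

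Three of seven rows clearly name another construct. Rows 5 to 7 are open to argument and are left out of the count.

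**Could this be a column that slipped when the PDF was read?** The measure for row 3 sits in row 1, so it would have to move down two rows. The measures that fit row 1 sit in rows 3 and 4, so they would have to move up two or three. The measure for row 4 sits in row 7, three rows up. Row 2 needs no move. These moves go in opposite directions, so no single shift repairs the table. The right-hand column begins in the order in which section 3.7 lists the toolkit's constructs. The likely origin is therefore two separately ordered lists placed next to each other.

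**Are the constructs collected at all?** Yes. Section 3.7 includes acceptability, adoption, penetration and sustainability, and row 7 of the table includes satisfaction. The measure that fits each of the three rows is already in the same table.

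**Adherence after the intervention period**

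- Section 3.5 item 4 names NPT and nothing else. CRF 3 makes it a staff survey.
- The audit in section 7.2 runs within the 31-month phase, which the milestones table dates September 2023 to March 2026.
- The deviation rule in sections 7.1 and 8.3 states no period.
- In Phase III of the milestones table, the sustainability assessment lists staff and consumer interviews only.
- The same phase plans observational data from April 2026 to April 2027, but no passage links the deviation count to them.

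The audit therefore ends as the post-study period begins, and the only measure expressly assigned to adherence in that period is the survey.

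**CRF 2.** GenPrem's eight domains are convenience, communication, quality, environment and facilities, integration, involvement, discomfort and patient-centred care. None is cost or quality of life. Elsewhere, section 7.1 has twelve parents per hospital complete the proxy PedsQL and records out-of-pocket expenses and lost income. The parent interview in section 7.2 covers income interruption and out-of-pocket costs, and section 8.3 takes social cost data from carers. The CRF 2 source line is therefore incomplete, but the data are planned.

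**The case against.** The strongest reply is that nothing is lost. All the toolkit constructs are collected, so the table contains a labelling slip that a careful analyst would notice. That is largely right about the data. It does not remove the point, because the table states the pairings, and an analyst who followed them would publish under the wrong names.

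On adherence, it can be said that the deviation rule has no end date and that post-study data are planned, so the rule could be read as covering them. NPT also fits the sustainability half of item 4, since section 6.2.3 describes it as concerned with practices embedded in everyday work. Both observations stand. They leave the adherence half of the item with an explicit assignment to a survey and only an implied one to chart data.

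A reader might infer that these outcomes would go unmeasured, that there would be no quality-of-life score, or that the societal evaluation would lack cost data. The documents do not support this. The toolkit covers the constructs, and PedsQL and the parent cost items are planned in sections 7.1, 7.2 and 8.3. A reader might also infer that the regression on implementation depth is compromised. Neither section 7.2 nor section 8.3 defines depth by the mis-paired rows, so no such effect is shown.

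**Conclusion.** The point holds as an error of assignment. Three of seven implementation outcomes carry the instrument of a different construct, and one secondary outcome, adherence beyond the intervention period, is expressly tied only to staff opinion. The effect is mislabelled results on implementation outcomes, including acceptability under objective 3, and a weak basis for any claim about adherence after the study. The CRF 2 entry is a minor inconsistency. The primary outcome, the sample size and the transfer analysis are untouched.

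Two assumptions matter. The toolkit's measures are judged by their names, because their content is not in the protocol. The adherence remedy assumes that the post-study observational data will hold the chart items needed to count deviations. Appendix 4 still carries open drafting questions about what that period will observe, so this should be confirmed.

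**What to change.** 1. In the section 8.3 table, pair routine use with the adoption and penetration measures, acceptability with the acceptability measure, and satisfaction with use with the satisfaction measure.
2. In section 3.5 item 4, state that adherence after the study is measured by the deviation measure already defined in sections 7.1 and 8.3, applied to the April 2026 to April 2027 observational data. Keep the NPT survey for normalisation and sustainability, and add the deviation measure to the Phase III sustainability assessment in the milestones table.
3. As a consistency edit, list PedsQL (quality of life) and the parent cost items (out-of-pocket costs) beside GenPrem (experience) as sources for CRF 2 in section 7.1.

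The cost is changes of wording and some further abstraction from records that the study already plans to collect. No new instrument or parent contact is needed.

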9. ADVERSE EVENTS AND RISKS

9.1 Adverse Event Definitions

Adverse Event (AE)

Adverse event data is collected as part of the study design and will form part of the secondary outcomes of the study. Conditions that are present at screening and do not deteriorate will not be considered adverse events. These outcomes will be routinely reported via standard hospital internal reporting methods/risk management processes. If any of the attending clinicians suspect an adverse event that is related to the study design, such an adverse event will be immediately reported to the Chief Investigator and Townsville HHS HREC.

For the purposes of this study the site investigator is responsible for recording all AEs, regardless of their relationship to study intervention. Conditions that are present at screening and do not deteriorate will not be considered AEs.

Serious adverse event (SAE)

SAEs for this study are defined as:

- Hypoxaemia leading to cardiac massage which the clinician believes is related to one of the study interventions
- Cardiac arrest: Loss of spontaneous cardiac output
- Mortality (all events will be reported)
- OR any life-threatening medical event or reaction which the clinician believes may be study related

Adverse event (AE)

AEs are defined as but limited to the following:

- Severe hypoxaemia with saturations <80% for longer than 1 minute
- Pneumothorax
- Unexpected need for endotracheal tube placement
- Bradycardia: bradycardia not requiring treatment; bradycardia of <60/min [27, 28]

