9.2 Reporting of SAEs

All SAE data will be recorded on a SAE form on the CRF and submitted to the Townsville HHS HREC within 24-72hrs, in accordance with the safety reporting policy of HREC. Information reported will include: patient initials and study number, nature of the event, start and end time of the event, investigators opinion of relationship between implementation of the respiratory care bundle and the event (unrelated, possibly, probably or definitely related). Notification to the Townsville HHS HREC and their response may require amendment/s to the respiratory care bundle. If this occurs the necessary changes will be made.

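### Two of the four serious adverse event definitions require the clinician to believe the event is study related, so SAE counts for those events are not comparable between control and intervention phases

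*Protocol*

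**What the plan says.** Protocol section 9.1 lists four kinds of SAE. Two depend on the clinician's view of cause:

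- "Hypoxaemia leading to cardiac massage which the clinician believes is related to one of the study interventions"
- "OR any life-threatening medical event or reaction which the clinician believes may be study related"

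Two do not:

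- "Cardiac arrest: Loss of spontaneous cardiac output"
- "Mortality (all events will be reported"

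For adverse events (AEs) in general, the same section says that "the site investigator is responsible for recording all AEs, regardless of their relationship to study intervention". It also makes AE data part of the secondary outcomes. Section 9.2 sends SAEs to the ethics committee within 24-72 h, with the investigator's rating of the relationship to the bundle: "unrelated, possibly, probably or definitely related". Section 9.3 gives seriousness and relationship as separate fields in the description of each AE. The key to Figure 2 in section 4.1 defines a control-phase cluster as one not exposed to the intervention, and says that data are captured in both control and intervention phases.

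**The concern.** A stepped wedge compares outcomes in control months with outcomes in intervention months, so an event has to be defined in the same way in both. A definition that asks whether the study caused the event cannot meet that condition when one phase contains no study intervention. After crossover, the answer comes from staff who have just been trained in the bundle and know which phase they are in.

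This trial intends to keep more sick children in local hospitals. Section 9.5 names delayed transfer of a child who needs higher-level care as a potential risk. The harm to look for is therefore deterioration at the local site, which a clinician may reasonably put down to the illness. Under the two conditional definitions, such an event is then not an SAE. Adverse effects are also a listed outcome (section 3.6, item 7), and section 9.5 gives a data safety monitoring board the task of following the trajectory of outcome. Both need counts that mean the same thing in each phase.

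**Working it through.** No arithmetic applies; the check is a comparison of texts.

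1. **Count the conditions.** Of the four SAE items in section 9.1, two require the clinician's belief in relatedness (hypoxaemia leading to cardiac massage; any life-threatening event) and two do not (cardiac arrest; death).

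2. **Apply the four items to each event type and phase.**

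| Event | Control phase | After crossover |
|---|---|---|
| Death | SAE | SAE |
| Loss of spontaneous cardiac output, with or without massage | SAE | SAE |
| Hypoxaemia with cardiac massage, output not lost | In effect not an SAE: no study intervention to attribute it to | SAE only if attributed |
| Life-threatening event short of arrest or death | In effect not an SAE, for the same reason | SAE only if attributed |

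The words 'in effect' are needed because the protocol does not say what study intervention or study related would mean in a control month.

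3. **Compare with the rule for AEs.** Section 9.1 requires AEs to be recorded whatever their relationship to the intervention. Capture is separated from causality for AEs, but not for two of the four SAE items.

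4. **Compare with the rating on the form.** Sections 9.2 and 9.3 have relatedness graded once an event is reported, with unrelated as an option. For the two conditional items, an event reaches the form only because someone already believed it was related, so the lowest grade has little use there.

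5. **Check what catches an event that is not attributed.** It may be recorded as an AE with severity, seriousness, treatment, outcome and relationship (section 9.3). Three limits apply:
   - Section 9.3 gives no criteria of its own for seriousness, so the only guide is the SAE list in section 9.1.
   - The lead-in to the AE list is garbled and can be read as closed or as open. If closed, a life-threatening event that matches none of its four items is on neither list.
   - The immediate report to the Chief Investigator and ethics committee in section 9.1 also depends on a suspected link to the study, so it does not fill the gap.

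**The case against.** The strongest case for the plan is that little is lost. Deaths and cardiac arrests are SAEs in every phase, and hypoxaemia that leads to massage will often also be an arrest. Severe hypoxaemia, pneumothorax and unexpected intubation are AEs with no relatedness condition, so they can be compared between phases as they stand. The outcome in section 3.6 speaks of adverse effects and is not tied to the SAE label. There is also routine hospital incident reporting (9.1), the monitoring board (9.5) and safety review by the site investigator (section 11).

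Most of this stands, and it rules out several stronger readings that a reader might infer:

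- **That the same event is always an SAE after crossover and never in control.** The text does not support this. After crossover it must still be attributed, and arrest and death count in both phases.
- **That sections 9.1 and 9.2 flatly contradict each other.** They do not. The recording rule governs AEs, and the unrelated grade has a clear use for arrests and deaths. The belief that admits an event is the clinician's, while the grade is the investigator's, so the two could differ. The fit is poor, but both rules can be followed.
- **That these events disappear.** They may well be in the AE records. What is lost is the SAE label and the 24-72 h route.
- **That the imbalance can be given as a number or a p-value.** The protocol states no rate for these events. A simple test on 1,260 children treated as independent would also ignore the intracluster correlation of 0.1 assumed in section 8.1.
- **That unexpected intubation is wrongly classed as an AE.** The protocol places it there and contradicts itself nowhere on the point; moving it would be a preference.

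The objection does not remove the phase-dependent label itself, or the dependence on unblinded opinion after crossover.

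**Conclusion.** The concern holds within limits. Two of the four SAE definitions cannot be applied alike in control and intervention months. The events affected are life-threatening events short of arrest or death, and cardiac massage without loss of output. For these, SAE counts should not be compared between phases. A difference could reflect the definition and the clinician's attribution rather than the care, in either direction. Reporting to the ethics committee within 24-72 h is likewise incomplete for events that are not attributed to the study.

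This rests on three assumptions: the definitions are applied as written, treating staff know their phase (they are trained during the transition month), and control-phase clinicians find nothing in the study to attribute an event to. The number of events affected is unknown.

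The bradycardia item, "Bradycardia: bradycardia not requiring treatment; bradycardia of <60/min", is a separate and smaller wording matter. Whether bradycardia that did need treatment, at 60/min or above, is covered depends on whether the AE list is closed or open, which its lead-in leaves unclear.

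**What to change.** - In section 9.1, delete the clause about the clinician's belief from the hypoxaemia item and from the life-threatening item.
- State that the same SAE list applies in control, transition and intervention months.
- Grade relatedness only after capture, on the forms already described in sections 9.2 and 9.3.
- Reclassify events already recorded against the amended list, in every phase.
- Reconcile the wording of the AE list: say whether it is closed or open, and make the bradycardia item consistent with that.

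This is a wording amendment to section 9.1 and the case report form. It changes no treatment, sample size or randomisation. The cost is some more SAE forms, mostly graded unrelated, and a pass through existing records. If an event was never entered as an AE because the list was read as closed, finding it would mean returning to the medical records, which section 7.1 already names as the source of the clinical data.

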3.6. Secondary Health Service Research Outcomes

The *health service research outcomes* are:

1. Reduced health care resource utilisation in the form of reduced hospital transfers for higher level of care.
2. Satisfaction with education and competencies associated with ARF management
3. Electronic medical record prompts are operational
4. Use of evidence-based-practice (EBP) is cost-effective
5. Patient/Carer satisfaction
6. Availability of the associated materials, which are cost-effective
7. Reduced adverse effects for children with ARF or other outcomes.

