9.3 Assessment and documentation of adverse events

The description of each AE on the CRF will include all of the following:

- Description of the AE
- Onset date, duration, date of resolution
- Severity (mild, moderate or severe)
- Seriousness
- Treatment/Management/Action taken
- Outcome (recovery, death, continuing, worsening)
- Likelihood of relationship of AE to the study treatment (Unrelated, Possible, Probable, Definite).

Changes in the severity of an AE will be recorded on the CRF.

AEs characterised as intermittent will be documented for each episode.

All AEs will be followed to adequate resolution or stabilisation, where possible.

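### Two of the four SAE categories in 9.1 count only if judged study related, so any control-versus-intervention comparison using those two labels is tilted against the bundle

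*Protocol*

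**What the plan says.** Section 9.1 gives adverse events an outcome role: "Adverse event data is collected as part of the study design and will form part of the secondary outcomes of the study". Section 3.6 item 7 gives the hoped-for direction: "Reduced adverse effects for children with ARF or other outcomes".

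Section 9.1 then lists four SAE categories. Two need an attribution by the clinician:

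- "Hypoxaemia leading to cardiac massage which the clinician believes is related to one of the study interventions"
- "OR any life-threatening medical event or reaction which the clinician believes may be study related"

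The other two are cardiac arrest, defined as loss of spontaneous output, and death. Neither depends on attribution.

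AEs are handled differently. Section 9.1 has the site investigator record all of them whatever their relationship to the intervention, and section 9.3 gives each AE one field for seriousness and another for relationship. The AE list itself opens with "AEs are defined as but limited to the following" and names severe hypoxaemia, pneumothorax, unexpected intubation and bradycardia.

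The key to Figure 2 (section 4.1) describes control-phase clusters as unexposed to the intervention and says data are captured in both phases.

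**The concern.** In a stepped wedge trial, every outcome that is compared between phases needs an entry rule that works the same way in both. For two SAE categories the rule asks whether the event is, or may be, due to the study. A clinician at a hospital still giving its usual care has almost nothing to attribute the event to. The same event in the same kind of child can therefore be an SAE after rollout and not before it.

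The clinician also knows the phase. Section 4.1 places a month of staff training immediately before each hospital's intervention phase.

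At stake is the reading of the safety outcome. The protocol hopes to show fewer adverse effects, and a comparison using these two labels could show a rise where there is none, or mask a real fall.

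**Working it through.** The protocol gives no SAE rate and no SAE comparison, so there is no figure to reproduce. The check is one of definitions.

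**Step 1. Does each SAE category depend on attribution (9.1)?**

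| SAE category | Needs clinician attribution? | Same rule in both phases? |
|---|---|---|
| Hypoxaemia leading to cardiac massage | Yes, to a study intervention | No |
| Cardiac arrest | No | Yes |
| Death | No | Yes |
| Any life-threatening event | Yes, may be study related | No |

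Two of the four carry the clause.

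**Step 2. Can the condition be met in control months?** For the massage category it cannot sensibly be met, because no study intervention is in use. The wording of the life-threatening category is looser, so a control-month event is not strictly impossible, only unlikely.

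**Step 3. Direction.** Let *f* and *g* be the shares of true events in a conditional category that are attributed to the study in intervention and control months. Then

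labelled ratio = true ratio × *f*/*g*.

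Whenever *g* is smaller than *f*, the labelled intervention/control ratio exceeds the true one. As *g* approaches zero, the control count for these labels vanishes whatever the true rate. Neither *f* nor *g* is in the protocol, so the direction follows but the size does not. If the clause is removed, *f* = *g* = 1 and the labelled ratio equals the true ratio.

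**Step 4. How much do other sections recover?**

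- Massage events will often also be cardiac arrests, which count unconditionally, or will meet the severe-hypoxaemia AE. The clause therefore bites mainly on the life-threatening category.
- The four listed AEs carry no attribution clause and remain comparable.
- The seriousness and relationship fields in 9.3 help only if the event is recorded as an AE. Read literally, the AE list is closed, and a life-threatening event that is off the list and judged unrelated has no category at all. If the list was meant to be open, the event is recorded as an AE but is still not an SAE.

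The recovery is real but partial. None of these provisions takes the clause out of the SAE definition.

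**The case against.** The strongest reply is that no section plans a pooled SAE total or an SAE rate by phase. The models in 8.2 cover transfers and length of stay. The stated use of the SAE form is reporting to the ethics committee (9.2), for which an attribution filter can be reasonable. The stated outcome is adverse event data, which are recorded regardless of relationship. What is left is a narrow group: life-threatening, neither death nor arrest, off the AE list and judged unrelated. How safety is tabulated may properly sit in an analysis plan that is not shown.

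Much of this stands and limits the point to comparisons that use the two labels. It does not remove it. The protocol makes adverse event data an outcome, names a reduction as the aim, and itself fixes the definition under which SAEs are classified.

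Three stronger readings are tempting, and the document does not support them.

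- *Section 9.2 contradicts 9.1 by allowing an unrelated grade.* It does not. Section 9.1 turns on what the clinician believes, whereas 9.2 records the "investigators opinion of relationship between implementation of the respiratory care bundle and the event (unrelated, possibly, probably or definitely related"). These are separate judgements that may differ, and the unrelated grade is needed anyway for deaths and arrests.
- *The SAE count will be inflated by some stated factor.* Any multiplier would rest wholly on assumed attribution shares, and a pooled total would also need an assumed mix of categories.
- *The clause makes the bundle look safer than it is.* An intervention-month event put down to the disease does lose its SAE label, but a control-month event loses it more readily. In the phase comparison the tilt therefore runs against the bundle.

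**Conclusion.** The point holds in limited form. Two of the four SAE categories have an entry rule that depends in practice on the phase, so a control-versus-intervention comparison using those labels is tilted against the bundle. This rests on one assumption: clinicians attribute control-month events to the study less often than intervention-month events. That is close to certain for the massage category and very likely for the life-threatening one.

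The size cannot be derived from the document. Deaths, cardiac arrests, the listed AEs and the primary outcome are unaffected. This is a minor-to-moderate flaw in a secondary safety outcome, worth correcting because it is a stated rule and the correction is cheap.

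**What to change.** For the adverse-event secondary outcome (3.6 item 7 and 9.1), delete the two relatedness clauses and count all four SAE categories in both phases regardless of attribution. Keep relatedness as the separate field that 9.2 and 9.3 already provide (for AEs, "Likelihood of relationship of AE to the study treatment (Unrelated, Possible, Probable, Definite")) and use it for reporting to the ethics committee. Correct the opening of the AE list to *but not limited to*.

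Apply the same rule to months already collected. Figure 2 starts data capture in September 2023 and has the first cluster in its intervention phase from April 2024, while protocol V3.0 is dated July 2024. A change going forward only would split the data between two definitions. Section 7.1 takes clinical data from the medical records, so earlier events can be found there.

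The costs are some re-ascertainment of those months, and more events that reflect the course of the disease. The latter are counted by the same rule in both phases, so they add noise but no tilt. The relatedness field needs no new data collection.
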